# Note for recruiting sites

The best place to access quick-reference, up to date methodological information is 'Study Guide for Recruiting Sites' and 'Sampling Guide for Recruiting Sites' in the ISF

# 1. Version Control Table

Version	Author/approved by	Date	Summary	
V0.1	[name]	31 January 2023	First Draft	
V0.2	[name]	12 February 2023	Second Draft	
V0.3	[name]	20 February 2023	Third Draft	
V0.4	[name]	23 February 2023	Fourth Draft	
V0.5	[name]	02 March 2023	Fifth Draft for Peer Review	
V0.6	[name]	26 March 2023	Sixth Draft responding to Peer Review	
V1.0	[name]	29 March 2023	Submitted for REC meeting to be held on 14 April 2023	
V2.0	[name]	18 May 2023	Submitted to REC 18 May 2023 following feedback	
V2.1	[name], [name]	4 July 2023 and 25 July 2023	Study Amendment - Removal of Buccal Swab as a sample - Revision of inclusion / exclusion criteria - Correction of minor typographical errors	
V3.0	[name]	28 July 2023	Submitted to REC 28 July under GSAM001	
V3.1	[name], [name], [name], [name]	28 October 2023	Study amendment  - Updated sampling strategy - Removal of baby exclusion if born < 36 weeks gestation (facilitating inclusion of babies born prematurely) - Death of birthing parent pathway updated based on external legal advice - Updated for publication of conditions list - Updated to reflect our approach to unanticipated events - Updated modelling	
V4.0	[name] and [name]	1 November 2023	Submitted to REC 3 November under GSAM002	

V5.0	[name], [name], [name]	3 October 2023	Submitted to REC under GSAM006	
V6.0	[name]	17 December 2024	Submitted to REC GSAM008	
V7.0	[name]	21 March 2025	Submitted to REC GSAM009	
V8.0	[name]	02 December 2025	
 
Addition of PBMC sample processing
 
Clarification around a baby being born at a different hospital than planned
 
Updated temperature range for sample processing at site
 
Correction of typos
 
	

# 2. Protocol Synopsis

# **Background**

#### Genomics in healthcare

Genomics is playing an increasing role in healthcare, with the UK at the forefront of its implementation, building on historical excellence together with recent progress such as the 100,000 Genomes Project and the creation of the NHS Genomic Medicine Service and the National Genomic Research Library. The role of genomics is currently most prominent in diagnostics where it is now part of routine care for rare conditions and cancer. Its role is growing in preventative and predictive care, most notably through pharmacogenomics. Translational research is exploring potential roles in other areas such as polygenic risk scores.

The advent of next generation sequencing, and with it a new era of gene discovery and the routine use of whole genome sequencing in diagnostics, has had enormous impact for individuals with rare conditions. However, rare conditions remain a major cause of mortality and disability in high income countries.

Only ~10% of rare conditions have a treatment. However, there is real promise that, with the right research investment, infrastructure and regulatory frameworks, new precision treatments will change this.

In recent years there has been great interest in the possibility of routine newborn sequencing - particularly whole genome sequencing - to support screening, research and to be stored for future healthcare use. The potential value in these areas has been highlighted as well as the risks and complexities.

#### Newborn screening

Newborn screening is one of the success stories of modern healthcare, identifying rare conditions that are treatable early in childhood. However, generating the evidence to inform decisions on expansion of newborn screening is hard due to the rarity of the conditions. In the UK, nine conditions are currently screened for, predominantly using biochemical testing. Genomics plays only a small role, as a second tier test. The use of genomics presents the opportunity to look for a broader range (potentially hundreds) of rare conditions that are treatable early in childhood. We refer to this in this protocol as 'genomic newborn screening'.

A number of studies of genomic newborn screening are preparing to launch internationally, but there have been only three relatively small prospective studies that returned findings to participants. While these previous studies have given early insights, there remain many questions to explore in this complex area, from the right analytical approaches and test performance, methods of implementation, impact on outcomes (positive and negative) and workforce, as well as psychosocial implications, public attitudes and ethical questions.

### Supporting research

Discovery research, such as is now supported as part of routine genomic care in the NHS through the National Genomic Research Library, has had incredible impact in recent years, particularly on clinical diagnostics. However, there remain many urgent healthcare questions to address. Large scale research in 'unselected' cohorts of newborn babies has the potential to have real impact here, for example to better understand allele frequencies in children born today to improve diagnostics and screening, tracking the natural history of rare conditions or to identify those eligible for novel treatments early in the course of their condition. It also presents the opportunity for research on other analytical techniques for screening (e.g., tandem mass spectrometry and proteomics) and research across broader health questions (e.g., on common childhood disease).

Longer term storage of genomic data for reuse for healthcare

With the advent of next generation sequencing - and of whole genome sequencing in particular - the idea of generating genomic data once and reusing it to support a person's healthcare is increasingly discussed. It is possible to imagine that whole genome data generated at birth initially for newborn screening might be reused later for diagnostic testing, for example in a child who falls critically ill with features suggestive of a rare condition. As well as research to understand the potential costs and impacts of this approach, there are important questions to explore in terms of public attitudes, risks and broader implications of storing an individual's genome over their lifetime.

### Development, vision and objectives

Responding to these opportunities and questions, Genomics England was funded by the Department of Health and Social Care to co-design and run a research study on the potential value and costs, risks and benefits of offering whole genome sequencing to all newborn babies.

The Newborn Genomes Programme will be delivered by Genomics England in partnership with the NHS, underpinned by joint governance. The vision of the programme, developed with the Programme's NHS Steering Group is:

1. To evaluate the clinical utility, operational feasibility, acceptability and positive and negative impacts of screening for a larger number of childhood-onset rare genetic conditions in

- newborn babies using whole genome sequencing, and providing ongoing patient support and diagnostic and care pathways, through the Generation Study.
- 2. To support healthcare research and understand how, with consent, genomic and health data could be used for research in the newborn setting to enable new diagnostic discoveries and treatments to be developed
- 3. To explore the potential risks, benefits, and broader implications of storing an individual's genome over their lifetime (e.g., potential for preventative steps, personalised risk-based screening in later life etc.)

These will aims will be delivered through this protocol and the National Genomics Research Library Protocol. In joining the Generation Study, parents will be consenting to their child joining the research under both protocols.

This protocol focuses on the development of evidence to allow policy makers to decide whether and how whole genome sequencing should be offered to all newborn babies. The National Genomic Research Library Protocol will support broader research across all three aims of the study and be particularly crucial in supporting aims 2 and 3 where the emphasis is more on discovery than evaluation.

While all three of the broader study aims may drive policy and will be the focus of research questions investigated through this protocol, the most immediate policy focus is on newborn screening.

The research questions explored by the study (described in more detail in Section 13 and Appendix A) cover the following broad areas:

- 1. **Feasibility, acceptability and uptake.** Is genomic newborn screening feasible and acceptable and would it be broadly taken up if offered as part of routine care?
- 2. **Test performance and clinical utility.** What is the clinical utility of genomic newborn screening as evidenced by the number of screen-identified diagnoses likely to benefit from intervention compared to standard of care alone?
- 3. **Cost effectiveness and positive and negative impacts.** What is the cost effectiveness of genomic newborn screening compared to standard of care alone?
- 4. **Experiences and attitudes.** What are families' and stakeholders' experiences and attitudes to genomic newborn screening?

While it is important to emphasise the breadth of research questions necessary to support policy decisions and therefore explored through the study, we have also identified the following primary and secondary outcomes (each linked to one of the areas above).

The primary outcome is:

 To determine the clinical utility of genomic newborn screening as evidenced by the number of screen-identified diagnoses likely to benefit from intervention compared to standard of care alone.

The secondary outcomes are:

- To determine the feasibility and acceptability of genomic newborn screening in the NHS utilising mixed-method approaches to assess study implementation.
- To determine the cost effectiveness of genomic newborn screening compared to standard of care alone, supported by a health economic model developed to support the programme.

- To determine whether families' and stakeholders' experiences and attitudes are supportive of the adoption of genomic newborn screening.
- To determine any differential areas of positive or negative impact of genomic newborn screening related to indices of diversity including ethnicity and socio-economic deprivation.

# Methodology, delivery and sample size

Methodology and delivery

The Programme will be delivered in partnership with the NHS. The end-to-end patient journey is summarised in Figure 1 below.

Recruitment and sample collection will take place in NHS Trusts. All babies will undergo whole genome sequencing and receive results following analysis for a defined list of rare conditions that are treatable in childhood. Condition selection is governed by a set of agreed principles established by an expert Working Group following expert and public consultation, and under the oversight of an NHS Clinical Assurance Group that ensures relevant expert sign off of conditions, the availability of treatments and the capacity of clinical pathways. Modelling indicates that our approach will achieve a true positive to false positive ratio similar to existing newborn screening services.

[figure not shown]

11

Figure 1 - The participant experience

Comparator data will be drawn from age and gender matched children in two groups:

- a population comparator group of babies born at non-participating Trusts during the recruitment period of the study
- a rare conditions comparator group of children diagnosed with the study conditions nationally
  as identified through specialist clinical services and laboratories over a multi-year period with
  similar diagnostic genomic testing availability to the study period

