# Sample size

Determination of sample size was aligned to the primary outcome of the study, to determine clinical utility of genomic newborn screening, and focusing on one component of it - evidence of the potential incidence range of genetic diseases where early intervention is likely to improve outcomes in newborns in the UK population. As set out in Sections 6 and 13 in more detail, the primary outcome is one of a suite of strands of evidence that the study aims to generate to support policy decisions in this area.

The work carried out by the Genomic Analysis in Children Task and Finish Group estimates that between 1 in 457 and 1 in 686 live births would be affected by a disorder that:

- Is not part of current newborn screening
- Has a treatment available within the first five years of life that impacts substantially on mortality or morbidity

The required number of participants to be 95% certain that the incidence estimate from the study will be between the middle point of an estimate, 1/572 +/- 6% error, is approximately 105,000.

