The sample size calculation to estimate this incidence of genetic diseases was based on the normal approximation to the binomial distribution with simple random sampling assumed . For the sample size calculations the proportion of subjects screened positive was assumed to be 0.011, and it was derived from an estimate of the true population incidence, the middle point of the estimate, 1/572, by using the sensitivity of detection of 65% and specificity of detection of 99% . Dropout rate was assumed to be 10%. The sensitivity of detection of 65% and specificity of detection of 99% used in calculations is the lower bounds of the estimates obtained during bioinformatics prioritisation algorithm modelling. Expected specificity is discussed in more detail in Section 10. We note that sample size calculations for estimating prevalence in rare conditions are highly sensitive to the assumptions of test performance metrics, in particular the assumption on specificity . Therefore we will update the calculations before the study, when the list of conditions is finalised and sensitivity and specificity modelling for those conditions is complete, as well as monitor and update throughout the study. In addition, throughout the study we will be updating the calculations to monitor that the sample size is sufficient to evaluate expected study-wide true positive rate. See section 13 for more information.

To validate the sample size calculations further and to understand the behaviour of sample size in relation to other parameters, Monte Carlo simulations using a range of true population incidence, sensitivity and specificity were performed. An example of simulation, assuming 65% sensitivity, 99% specificity and 1/572 true incidence is depicted in Figure 5.

Figure 5 - An example of the Monte Carlo simulation of two-sided 95% confidence interval for the proportion of subjects screened positive assuming 99% specificity and 65% sensitivity. For each value in the sample size, the expected proportion of subjects screened positive was computed from a binomial distribution 15 000 times. The final confidence interval is obtained by clipping 95% of the values among the 15 000 (filled area). The dashed lines show the maximum and minimum values of the obtained proportion of subjects screened positive for each sample size. The dotted lines indicate the expected proportion of subjects screened positive +/- 6% error margin.

[figure not shown]

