## Variant phasing

We note that because the study will not collect parental samples up front, in some cases it will not be possible to determine whether the variants found in a baby follow the expected mode of inheritance because short read technology does not enable phasing heterozygous variants unless they are in close proximity (within the same fragment). To quantify this we have performed modelling in ~35,000 adult individuals in the National Genomic Research Library largely recruited for reasons other than a rare condition. This analysis showed that this scenario, where candidate high risk compound heterozygous variants in biallelic genes will be indistinguishable from two heterozygous variants in cis will be expected only in ~0.1% of participants, and therefore will not cause a major increase in false positive cases. For the cases where it is not possible to distinguish cis and trans phases, the follow up testing will be arranged to determine the phase using the most appropriate method (e.g. inheritance analysis in a family, or long read sequencing). This, depending on condition and urgency of testing and possible interventions, may be done before or in parallel to other orthogonal testing, such as metabolic testing.

We will continuously monitor and fine tune the performance of automated filtering to incorporate new knowledge about conditions, genes and variants, as well as adapt to sequencing technology and alignment and variant calling specifics (e.g., remove recurrent technical artefacts).

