# Modelling to guide the variant prioritisation strategy

To test our assumptions and chosen strategy, we modelled our approach using a dataset of ~35,000 adult individuals in the National Genomic Research Library largely recruited for reasons other than a rare condition. While the list of conditions and genes is not finalised, for the initial analysis we use the gene list available at rx-genes.com (July 2022). A total of 739 genes with different modes of inheritance (148 autosomal dominant, 484 autosomal recessive, 66 dual modes of inheritance and 41 X-linked) were included in this exploratory analysis. We note that a considerably smaller number of genes are going to satisfy condition selection principles, therefore our initial analysis is overestimating expected numbers of potential false positives and represents the "worst case" scenario e.g., some of the genes in the Rx-genes database are associated with low penetrance or have variable or later onset, and therefore pathogenic variants in those genes are expected to be detected. However, for simplicity and to estimate "the worst case" we included all genes and assumed all individuals that carry variants that would be reportable as pathogenic or likely pathogenic were false positives following the automated process but prior to manual interpretation. Depending on the strictness of criteria used in filtering, we achieved 98-99.5% study-wide specificity from automated filtering outputs.

The specificity further increased after light-touch manual curation of automated outputs e.g., for autosomal recessive genes, the variants in 46% of samples were reclassified as non-reportable during manual review, e.g. because they were obvious technical artefacts or because they were reclassified as variants of unknown significance (such as some predicted loss of function variants in the last exons, or previously reported ClinVar likely pathogenic variants with insufficient evidence).

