For autosomal recessive genes, the specificity after manual curation reached 99.8%. The lower specificity for autosomal dominant genes (98.2% before manual curation) was heavily driven by a small number of genes with a large number of pathogenic or likely pathogenic variants in ClinVar, with just two genes accounting for 25% of samples, and 15 genes accounting for 70% of the samples with P/LP variants. Upon inspection, none of those genes are likely to pass conditions framework principles to be included in the programme. Although many of the autosomal dominant genes will not pass conditions selection by failing principles because of low penetrance and/or age of onset, our specificity modelling will feed into analytical validity assessment and the genes that present a risk of materially reducing study-wide specificity will not be included.

We also note, that for a small number of individuals, where relevant phenotype data was available in the National Genomic Research Library, we were able to confirm the presence of the condition, and thus reclassify them as true positives, however we did not include those into the assessment, because the phenotype data was not available for the majority of individuals.

Based on this preliminary analysis, we estimate that the study-wide (i.e. for all genes combined) specificity of 99.5% or higher is achievable. The estimate of 99.5% specificity, assuming 65% sensitivity and study-wide conditions prevalence of 1:575. Reducing the gene list to the ones that satisfy conditions selection framework principles will further increase specificity. Of note, this modelling is based only on automated interpretation of results, and does not account for the effect of manual interpretation. We estimate that the number of children with a finding that would be returned to families would be <1%.

The data available from the Guardian study set out in Section 3 (Background) also provides useful estimation of the likely ratio of true positive to false positive findings at the point of returning findings to families. Analysis of the first 984 participants achieved a true positive to false positive ratio of

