#### In the situation of Partial Withdrawal:

- Samples and data will be processed as described in this protocol, and data from clinical records will continue to be linked to the baby's genomic and demographic information
- We will no longer contact the family. They will not receive exceptional findings, nor will they receive study updates or invitations to participate in Evaluation research.
- When babies whose parents have partially withdrawn turn 16, they will be actioned as full withdrawals - as we will not be able to contact and obtain consent for ongoing participation.

\*Exceptionally, parents may wish to withdraw the baby from the study after analysis of the genome sequence has started, but before screening results are made available. Because of the high threshold for positive predictive value of the screening results generated by the study, and in order to fulfil our duty of care to child participants, parents will be made aware that they will still receive study results should they partially or fully withdraw during this phase. Once screening results have been made available, the parent's wish to withdraw will be actioned. This aspect of the withdrawal process was specifically advised by the Newborns Ethics Working Group in January 2023. It is important to note that if a baby withdrawn during this period has a suspected condition, this case will still be referred into the clinical pathway, for confirmatory testing and ongoing clinical management.

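### Specificity is 99% for the sample size but 99.5% or higher for the reassurance, and no study-wide figure in the protocol demonstrates the high PPV it relies on

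*Protocol*

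**What the plan says.** The claim is in the synopsis (Methodology, delivery and sample size): "Modelling indicates that our approach will achieve a true positive to false positive ratio similar to existing newborn screening services". Section 10 (Overall approach) makes high PPV and such a ratio the aim of the reporting strategy. Section 15 cites PPV as one ground for still giving results to families who withdraw during analysis: "Because of the high threshold for positive predictive value of the screening results generated by the study". The only benchmark is in Section 3, where metabolic programmes are said to run from 10:1 to 1:5 true to false positives.

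The figures beneath these statements come from two places.

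- **Section 6, Sample size.** "the proportion of subjects screened positive was assumed to be 0.011". This is derived from a prevalence of 1/572, 65% sensitivity and 99% specificity. The last two are described as lower bounds from modelling of the prioritisation algorithm. With ±6% error and 10% dropout, the result is about 105,000.
- **Section 10, Modelling to guide the variant prioritisation strategy.** "we achieved 98-99.5% study-wide specificity from automated filtering outputs". The text then calls 99.5% or higher achievable. The next sentence pairs 99.5% with its inputs, "assuming 65% sensitivity and study-wide conditions prevalence of 1:575", and stops without giving a result. Later comes "We estimate that the number of children with a finding that would be returned to families would be <1" per cent, which Section 11 repeats.

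On babies whose two variants cannot be phased, Section 10 (Variant phasing) says this "will be expected only in ~0.1% of participants, and therefore will not cause a major increase in false positive cases".

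**The concern.** The same modelling is cited for three purposes with figures that do not match. The sample size uses 99% and 1.1% positive. The reassurance to families and clinical services uses 99.5% or higher and under 1%. The modelling text itself goes down to 98%, below the 99% that Section 6 calls the lower bound.

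At a prevalence near 1 in 570, the true-positive to false-positive ratio is governed almost entirely by the last fraction of a percentage point of specificity, so these differences are not cosmetic. The ratio is also a main output of the interim analyses in Section 13. No expected value has been derived for it, so an interim result can be held only against a quoted range of 10:1 to 1:5, which is fiftyfold wide.

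**Working it through.** **Inputs.** Sensitivity (Se) is 0.65 and prevalence (π) is 1/572, with a stated range of 1/457 to 1/686 (Section 6). Specificity (Sp) is 99% (Section 6), 98% to 99.5% (Section 10, automated) and 99.8% (Section 10, recessive genes only, after manual curation).

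**Reproducing the plan's figure.** The screen-positive proportion is p = Se·π + (1 − Sp)(1 − π) = 0.65/572 + 0.01 × 571/572 = 0.001136 + 0.009983 = 0.01112, which is the stated 0.011. With ±6% applied to p, as in the Figure 5 caption, N = 1.96²·p(1 − p)/(0.06p)² = 94,902. Dividing by 0.9 for dropout gives 105,447, which agrees with about 105,000.

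**Ratio, PPV and positive fraction.** TP rate = Se·π, FP rate = (1 − Sp)(1 − π), PPV = TP/(TP + FP). At Se 65% and 1/572:

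| Specificity | Source | FP per TP | PPV | Positive |
|---|---|---|---|---|
| 98% | Section 10, low end | 17.6 | 5.4% | 2.11% |
| 99% | Section 6 | 8.8 | 10.2% | 1.11% |
| 99.5% | Section 10, achievable | 4.4 | 18.5% | 0.61% |
| 99.8% | Section 10, recessive only; study-wide use is an assumption | 1.8 | 36.3% | 0.31% |

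Using 1/575, as Section 10 does, leaves the 99.5% row unchanged to the digits shown. Over the stated prevalence range, the 99.5% ratio runs from 3.5 FP per TP (1/457) to 5.3 (1/686).

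**Specificity needed.** At Se 65% and 1/572, under 1% positive needs more than 99.11%, and a ratio of 1:5 needs 99.43%. The 99% in Section 6 fails both and 99.5% passes both.

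**Is the 65% to blame?** Not mainly. At 100% sensitivity, 99% gives 5.7 FP per TP and 99.5% gives 2.9 (PPV 26%).

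**Precision.** After dropout, 105,000 × 0.9 = 94,500. Relative error = 1.96·√[(1 − p)/(p·94,500)].

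- At 99%, p = 0.01112: 1.96 × √(0.98888/1,050.8) = 6.0%.
- At 99.5%, p = 0.00613: 1.96 × √(0.99387/579.1) = 8.1%.

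A low specificity is therefore not the cautious choice in this formula, because it raises p and makes the relative error look smaller.

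**Unresolved phase.** 0.1% ÷ 0.1136% = 0.88 such babies per expected true positive.

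**The case against.** The strongest reply is that unlike stages are being compared. The 98% to 99.5% comes from automated filtering of a 739-gene list that Section 10 calls worst case. Every carrier of a reportable variant was counted as a false positive, and the genes that depress specificity most are not expected to be included. The ratio and the under-1% figure concern findings reported after manual review. That review removed 46% of recessive-gene samples. If the same share of all false positives were removed, which is an assumption, 99% would give 4.7 FP per TP, PPV 17% and 0.65% positive. At 99.5% it would give 2.4, 30% and 0.38%.

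This stands, and it limits the point. A reader might infer that the plan's figures contradict all three claims, or that the study will deliver a PPV under 20%. The document does not support either reading. At 99.5% the ratio lies inside the quoted range and under 1% is met, and a PPV under 20% as delivered would require manual review to remove nothing. High PPV is mostly worded as an aim. The 2:1 ratio in Section 10 is another study's result, not a commitment, so the 99.94% it would need here is no test of this plan. The unphased babies are not all false positives, follow-up phasing is planned, and they may already be counted in the specificity.

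Sections 6 and 10 also promise to redo the calculations, and Section 13 reviews the ratio at 1,000, 5,000, 20,000 and 50,000 participants. That helps, but Section 4 says the initial condition list was published in October 2023, and the current text still carries the preliminary figures.

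**Conclusion.** The point holds as an inconsistency and an undemonstrated claim, not as proof of poor performance. The 99% and 1.1% in Section 6 do not match the 99.5% or higher and under 1% in Sections 10 and 11, nor the 98% low end in Section 10. At 99% the implied ratio of 1:8.8 is worse than the worst programme quoted. At 99.5% the ratio of 1:4.4 is at the poor end of the range and passes just outside it, at 1:5.3, if prevalence is 1/686.

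The synopsis attributes its ratio to modelling, yet no post-review study-wide ratio or PPV is stated. Even the most favourable curated figure, 99.8% borrowed from recessive genes, gives 1:1.8 and a PPV of 36%. The stated ±6% becomes about ±8% at 99.5%.

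All this rests on the protocol's own sensitivity and prevalence, and on its formula applied to the screen-positive proportion.

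**What to change.** 1. Use one specificity, labelled as automated or after manual review, in Sections 6, 10 and 11. Correct the lower-bound description in Section 6 against the 98% in Section 10.
2. Reconcile 1.1% with under 1%, and restate the precision that 105,000 delivers at the chosen specificity.
3. Complete the unfinished sentence in Section 10 with its result: at 99.5%, 65% and 1:575, TP:FP is 1:4.4 and PPV is 18.5%.
4. Qualify the synopsis claim with the computed ratio and PPV across the stated specificity range. Add the post-review study-wide figure if it exists.
5. In Variant phasing, state whether the 0.1% is already counted in the specificity. Qualify the statement that it causes no major increase, giving the 0.88 per expected true positive and noting that not all would be false positives.

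The cost is protocol wording and a small table, with no change to study procedures. The drawback is that the stated expectations become less favourable.
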